9.10. Sensitivity analyses

Sensitivity analyses will be limited to the primary outcome and will consist of:

- Analysis adjusting for IDS and age, lactate, cardiac arrest and GCS at randomisation;
- Per-protocol analysis (population described in sections 5.3 and 5.4);
- An analysis to assess the effect of lactate timings Lactate clearance is calculated on measurements made at randomisation and 2 hours post-randomisation For this sensitivity analysis, time windows will be applied to the lactate measurements The lactate concentration at randomisation will only contribute to this analysis if the measurement was taken no more than 15 minutes (i.e. ≤15 minutes) before the PHEM team open the first transport box containing the allocated trial intervention The lactate concentration at 2 hours post randomisation will only contribute to this analysis if the measurement was taken within 30 minutes of the 2 hour assessment (i.e. between 1.5 and 2.5 hours post-randomisation) Lactate concentrations recorded outside these times will not be included in this sensitivity analysis
- An analysis to assess the effect of missing responses; missing responses will be simulated using a Markov chain Monte Carlo method (MCMC) to generate multiple datasets The imputation model will include the following variables: IDS, age, randomisation lactate, cardiac arrest, GCS, haemorrhage type, category of injury (penetrating, blunt, crush), heart rate, systolic blood pressure, and injury severity score Analysis will be then be performed on each set with the results combined using Rubin's rule to obtain a single set of results (treatment effect estimate and confidence intervals) Each component of the primary outcome will be imputed separately^{13,14}
- An analysis to assess the generalisability of the results by comparing baseline characteristics of those who are lost to follow-up or withdrawn from the trial with the trial

population

- An analysis to assess the generalisability of the results by comparing baseline characteristics of those who provide primary outcome data to those who do not provide primary outcome data

10. Analysis of sub-randomisations

Not Applicable

11. Health economic analysis

No health economic analysis is planned for this trial

12. Statistical software

Statistical analysis will be undertaken in the following statistical software packages: SAS v9.4 and RStan v2.19

13. References

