9.3. Handling missing data

In the first instance, analysis will be completed on received data only with every effort made to follow-up participants to minimise any potential for bias. To examine the possible impact of missing data on the results, and to make sure we are complying with the intention-to-treat principle, sensitivity analysis will be performed on the primary outcome measure.¹⁰ See section 9.10 for further details regarding planned sensitivity analyses.

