	Alcohol	n (%)	n (%)	n (%)	
	Other illicit substances	n (%)	n (%)	n (%)	
	Missing	n (%)	n (%)	n (%)	
Medical History					
ISS ³		Median (IQR)			
		Missing	n (%)	n (%)	n (%)
NISS ³		Median (IQR)			
		Missing	n (%)	n (%)	n (%)
Comorbidities	Yes	n (%)	n (%)	n (%)	
	No	n (%)	n (%)	n (%)	
	Missing	n (%)	n (%)	n (%)	
Anticoagulant medication	Yes	n (%)	n (%)	n (%)	
	No	n (%)	n (%)	n (%)	
	Unknown	n (%)	n (%)	n (%)	
	Missing	n (%)	n (%)	n (%)	
Antiplatelet medication	Yes	n (%)	n (%)	n (%)	
	No	n (%)	n (%)	n (%)	
	Unknown	n (%)	n (%)	n (%)	
	Missing	n (%)	n (%)	n (%)	

¹ Systolic blood pressure, Heart rate and Respiratory rate are summarised as continuous variables only for participants with non-zero on scene measurements

² Defined at those with a heart rate of 0 and blood pressure of 0

³ ISS and NISS will only be available for those participants who are TARN eligible, hence the number of missing participants refers to the number of TARN eligible participants missing their ISS or NISS.

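### The multiple-imputation model in SAP Section 9.10 leaves out randomised group, so the one missing-data analysis that re-estimates the treatment effect is pulled toward no effect wherever treatment affects the imputed component.

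*SAP*

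**What the plan says.** Section 9.3 bases the main analysis on observed outcomes ("In the first instance, analysis will be completed on received data only") and sends the reader to Section 9.10 for the missing-data check. Its stated purpose is: "To examine the possible impact of missing data on the results, and to make sure we are complying with the intention-to-treat principle".

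Section 9.10 gives the method: "missing responses will be simulated using a Markov chain Monte Carlo method (MCMC) to generate multiple datasets". The predictors are "The imputation model will include the following variables: IDS, age, randomisation lactate, cardiac arrest, GCS, haemorrhage type", then "category of injury (penetrating, blunt, crush), heart rate, systolic blood pressure, and injury severity score". That makes ten variables, all describing site, baseline state or injury. Each completed dataset is analysed, and the results are combined by Rubin's rule into a treatment effect estimate with its confidence interval. The item closes with: "Each component of the primary outcome will be imputed separately".

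Two further items in Section 9.10 bear on missing data. One compares the baseline characteristics of participants lost or withdrawn with those of the trial population. The other is described as "comparing baseline characteristics of those who provide primary outcome data to those who do not provide primary outcome data". Neither gives a treatment effect.

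**The concern.** An imputation model should contain every term of the analysis that will be run on the completed data. Here the analysis model contains randomised group and the imputation model, as listed, does not. Randomisation balances the listed predictors between arms on average, so the imputed event rate has the same expectation in both arms whatever treatment does. Mixing such values with observed ones dilutes any real difference.

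This matters because of what the analysis is for. It is the only planned analysis that re-estimates the effect with missing responses filled in. A reader will use it to judge whether missing data alter the result, and a built-in pull toward no effect would be hard to tell apart from a genuine effect of missingness.

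A second uncertainty is whether imputing the components separately means that each model ignores the other component. Under Section 9.4 a death before interval sampling counts as a lactate failure. A lactate model blind to survival would therefore draw survivors' values from a pool that includes those deaths.

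**Working it through.** **Inputs.** From Section 4.7: event rates of 71.7% (standard care) and 58.3% (PHBP), pooled 65%; 10% loss to follow-up; 490 participants; two-sided Fisher's exact test at 5%; 80% power. Allocation is 1:1 (Section 4.6). The SAP gives no figure for the share of primary outcomes that will be missing. Using 10% for it is an assumption, and 5%, 20% and 30% show the range.

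**The plan's own figures.** For 20% versus 10%, the continuity-corrected formula gives 219 per group, as stated, and 438/0.9 = 487, stated as 490. With 490 × 0.9 = 441, about 220 per group, exact Fisher power for 71.7% versus 58.3% is 81.8%, consistent with the stated 80%. The ratio 58.3/71.7 is 0.813, which the SAP gives as 0.82.

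**Case 1: whole composites missing at random, share m, imputed without arm.** Missing values in both arms are filled at the pooled rate, (71.7 + 58.3)/2 = 65.0%. So

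arm rate after imputation = (1 - m) × p(arm) + m × 65.0%

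and the risk difference is (1 - m) times its true value. At m = 10%:

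- standard care: 0.9 × 71.7 + 0.1 × 65.0 = 71.0%
- PHBP: 0.9 × 58.3 + 0.1 × 65.0 = 59.0%

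| Share missing | Standard care | PHBP | RR | RD (points) |
|---|---|---|---|---|
| 0% | 71.7% | 58.3% | 0.813 | -13.4 |
| 5% | 71.4% | 58.6% | 0.822 | -12.7 |
| 10% | 71.0% | 59.0% | 0.830 | -12.1 |
| 20% | 70.4% | 59.6% | 0.848 | -10.7 |
| 30% | 69.7% | 60.3% | 0.865 | -9.4 |

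With arm in the model, the first row is recovered under missing at random.

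**Case 2: only survivors' lactates missing, share q, imputed given survival but without arm.** A death is an event whatever the lactate (Section 9.4), so only survivors need a value. With mortality d, lactate failure f among survivors, and f* the value of f pooled over all survivors:

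arm rate = d + (1 - d) × [(1 - q) × f + q × f*]

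The component rates below are assumptions.

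- *Effect largely through lactate:* d = 43% versus 37%, f = 50% versus 34%. True rates are 71.5% and 58.4%, RR 0.817. Here f* = (0.285 + 0.2142)/1.20 = 41.6%. At q = 10% the rates are 71.0% and 58.9%, RR 0.829. At q = 20%, RR is 0.842.
- *Effect through mortality only:* d = 45% versus 30%, f = 40% in both arms. True rates are 67.0% and 58.0%, RR 0.866, RD -9.0. Since f* = f = 40%, imputation without arm leaves both unchanged.

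**Case 3: what each omission does.** A large-sample simulation took two positively correlated binary components (assumed rates and correlation), with 20% of lactate and 2% of mortality missing at random.

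| Imputation model | Standard care | PHBP | RR | RD (points) |
|---|---|---|---|---|
| Truth | 66.1% | 58.5% | 0.885 | -7.6 |
| Arm omitted only | 65.7% | 58.9% | 0.897 | -6.8 |
| Other component omitted only | 67.7% | 60.0% | 0.886 | -7.7 |
| Both omitted | 67.2% | 60.6% | 0.902 | -6.6 |

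Omitting arm shrinks the effect. Omitting the other component mainly raises the event rates.

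**The case against.** The strongest defence is that this is one sensitivity analysis. The primary estimate, interval and p-value come from received data and do not pass through the imputation. At 10% missing the shift is small and toward no effect, so it could not create a false claim of superiority. This stands, and it limits how serious the point is.

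It can also be said that an experienced programmer would add the treatment term unprompted. But the SAP sets out what the model will contain, and following it as written leaves arm out.

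On the components, the text speaks of one imputation model, and one such model can hold both. Separate imputation may mean only that the components are imputed instead of the composite. This stands: the wording is unclear, not plainly wrong, and the pull toward no effect does not come from there.

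A reader might go further and infer that the received-data analysis is biased the same way, so that agreement between the two would be false reassurance. Missing lactate does remove only survivors from the received data. The direction, however, depends on component rates that the SAP does not give. In the mortality-only example with 20% of survivors' lactates missing, the received-data rates are (0.45 + 0.176)/0.89 = 70.3% and (0.30 + 0.224)/0.86 = 60.9%. RR stays at 0.866 and RD moves to -9.4, slightly larger than the true -9.0.

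A reader might also object to injury severity score, given that "ISS and NISS will only be available for those participants who are TARN eligible". Imputation by MCMC can accommodate an incompletely observed covariate, so listing it is not an error. Adding further lactate measurements as predictors, or using logistic imputation, would be a matter of preference.

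**Conclusion.** The stated imputation model is wrong as written and should be corrected. It omits randomised group, is not said to be run by arm, and is then used to estimate a treatment effect.

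The Case 1 shrinkage, by about the missing share, assumes that whole composites are missing at random in equal proportion in both arms. On the SAP's rates and 10% loss this is a change of about 0.017 in RR and 1.3 points in RD, and it grows in proportion to the share missing. Where only survivors' lactates are missing, the size depends on how far treatment changes lactate failure among survivors, and it can be nil. The true missing share and the component rates are not in the document.

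The document does not support the conclusions that the primary analysis is invalidated by this fault or that both analyses must err in the same direction. The statement about separate imputation needs clarifying; if it means that the components ignore each other, the main consequence is inflated event rates in both arms.

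**What to change.** In Section 9.10, add randomised group to the listed variables, or state that imputation is carried out separately within each arm. State also that each component's imputation conditions on the other, in particular that missing lactate in survivors is imputed conditional on survival, and that the composite is derived from the completed components.

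The received-data analysis should stay primary. A rule letting the imputed estimate override it if the two differ is not needed, and without a threshold it would allow the choice to be made after seeing results.

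The cost is one or two sentences in the SAP and a changed imputation call, with no new data. The change should be dated before the imputation is run.

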Appendix A: Deviations from SAP

This report below follows the statistical analysis plan dated <insert effective date of latest SAP> apart from following:

Section of report not following SAP	Reason
<insert section >	<insert, e.g. exploratory analyses request by TMG>

Appendix B: Trial schema

PHEM doctor assesses patient at the trauma scene and confirms eligibility (see protocol section 4) for randomisation into the RePHILL Trial

Capillary lactate concentration measured immediately prior to intervention using a point of care device

PHEM doctor opens sealed transport boxes

Randomised Intervention

Fluid boluses will be given to restore a palpable radial pulse or a measured standard SBP above 90 mmHg

Crystalloid-based resuscitation arm:

Up to 4 boluses of 250 ml Sodium Chloride 0.9% (normal saline)
2 x 250 ml bags per box

Pre-hospital blood product resuscitation arm: Up to 4 units of PHBP given as follows:

1 unit PRBC → 1 unit LyoPlas
1 unit PRBC → 1 unit LyoPlas

Arrive at receiving hospital

Refer to protocol section 7

- Vital signs
- Standard coagulation and FBC
- Lactate clearance
- ROTEM[®] (designated sites)
- Platelet function (designated sites)

Informed consent for continued participation in the trial

Hospital admission

Inpatients will be followed-up for up to 30 days[†]

Presence/absence of ARDS

Organ dysfunction

Adverse event monitoring

[figure not shown]
Survival[‡]

Data cleaning & analysis

[figure not shown]
[†] For some mortality data will be collected up to discharge from the acute care setting which may be >30 days

[figure not shown]
Appendix C: Schedule of assessments

See trial protocol

Appendix D1: CONSORT flow diagram

Appendix D2: Baseline characteristics

		PHBP (n=xxx)	Crystalloid (n=xxx)	Overall (n=xxx)
Stratification variable				
Intervention Delivery Site	Midlands Air Ambulance (MAA)	n (%)	n (%)	n (%)
	MAGPAS	n (%)	n (%)	n (%)
	The Air Ambulance Service (TAAS)	n (%)	n (%)	n (%)
	East Anglian Air Ambulance (EAAA)	n (%)	n (%)	n (%)
Demographic and other baseline variables				
Gender	Male	n (%)	n (%)	n (%)
	Female	n (%)	n (%)	n (%)
	Missing	n (%)	n (%)	n (%)
Age, years	Mean (SD)			
	Missing	n (%)	n (%)	n (%)
Ethnic Group, n (%)	White (British)	n (%)	n (%)	n (%)
	White (Irish)	n (%)	n (%)	n (%)
	White (Other)	n (%)	n (%)	n (%)
	Black (Caribbean)	n (%)	n (%)	n (%)
	Missing	n (%)	n (%)	n (%)
Capillary lactate concentration (mmol/L)	Mean (SD)			
	Missing	n (%)	n (%)	n (%)
Mechanism of injury(ies) (More than one can apply)	Fall from <2m	n (%)	n (%)	n (%)
	Fall from ≥2m	n (%)	n (%)	n (%)
	Inhalation	n (%)	n (%)	n (%)
	Road traffic accident	n (%)	n (%)	n (%)
	Burn injury	n (%)	n (%)	n (%)
	Head Injury	n (%)	n (%)	n (%)
	Gunshot wound	n (%)	n (%)	n (%)
	Stabbing	n (%)	n (%)	n (%)
	Other	n (%)	n (%)	n (%)
	Missing	n (%)	n (%)	n (%)
Acute Brain Injury	Yes	n (%)	n (%)	n (%)
	No	n (%)	n (%)	n (%)
	Missing	n (%)	n (%)	n (%)
Mode of transport	Air	n (%)	n (%)	n (%)
	Ground	n (%)	n (%)	n (%)
	Missing	n (%)	n (%)	n (%)
Haemorrhage	Compressible	n (%)	n (%)	n (%)
	Non-compressible	n (%)	n (%)	n (%)
	Missing	n (%)	n (%)	n (%)
Category of injury	Blunt	n (%)	n (%)	n (%)
	Penetrating	n (%)	n (%)	n (%)
	Crush	n (%)	n (%)	n (%)
	Missing	n (%)	n (%)	n (%)
Tranexamic Acid				
Has the participant been given a tranexamic acid bolus?	Yes	n (%)	n (%)	n (%)
	No	n (%)	n (%)	n (%)
	Missing	n (%)	n (%)	n (%)
On-scene Vital Signs				
Systolic Blood Pressure ¹ (mmHg)	Zero	n (%)	n (%)	n (%)
	Non-zero	n (%)	n (%)	n (%)
	Missing	n (%)	n (%)	n (%)

		Mean (SD)			
Diastolic Blood Pressure ¹ (mmHg)	Zero	n (%)	n (%)	n (%)	
	Non-zero	n (%)	n (%)	n (%)	
	Missing	n (%)	n (%)	n (%)	
		Mean (SD)			
Heart Rate ¹ (bpm)	Zero	n (%)	n (%)	n (%)	
	Non-zero	n (%)	n (%)	n (%)	
	Missing	n (%)	n (%)	n (%)	
		Mean (SD)			
Respiratory Rate ¹ (/min)	Zero	n (%)	n (%)	n (%)	
	Non-zero	n (%)	n (%)	n (%)	
	Missing	n (%)	n (%)	n (%)	
		Mean (SD)			
Cardiac Arrest ²	Yes	n (%)	n (%)	n (%)	
	No	n (%)	n (%)	n (%)	
	Missing	n (%)	n (%)	n (%)	
Capillary oxygen saturation (SpO ₂) (%)		Mean (SD)			
GCS		Missing	n (%)	n (%)	n (%)
		Median (IQR)			
Suspected at time of injury	Missing	n (%)	n (%)	n (%)	
	Alcohol	n (%)	n (%)	n (%)	
	Other illicit substances	n (%)	n (%)	n (%)	
	Missing	n (%)	n (%)	n (%)	
Medical History					
ISS ³		Median (IQR)			
		Missing	n (%)	n (%)	n (%)
NISS ³		Median (IQR)			
		Missing	n (%)	n (%)	n (%)
Comorbidities	Yes	n (%)	n (%)	n (%)	
	No	n (%)	n (%)	n (%)	
	Missing	n (%)	n (%)	n (%)	
Anticoagulant medication	Yes	n (%)	n (%)	n (%)	
	No	n (%)	n (%)	n (%)	
	Unknown	n (%)	n (%)	n (%)	
	Missing	n (%)	n (%)	n (%)	
Antiplatelet medication	Yes	n (%)	n (%)	n (%)	
	No	n (%)	n (%)	n (%)	
	Unknown	n (%)	n (%)	n (%)	
	Missing	n (%)	n (%)	n (%)	

¹ Systolic blood pressure, Heart rate and Respiratory rate are summarised as continuous variables only for participants with non-zero on scene measurements

² Defined at those with a heart rate of 0 and blood pressure of 0

³ ISS and NISS will only be available for those participants who are TARN eligible, hence the number of missing participants refers to the number of TARN eligible participants missing their ISS or NISS.

Appendix D2a: Prehospital timeline by group

The duration in minutes between the time of the 999 call and prehospital events. Values above the diagonal correspond to the PHBP group and values below the diagonal correspond to the Crystalloid group.

Prehospital event	999 Call	On-scene attendance	Randomisation Capillary Lactate	Treatment box opening	Left Scene*	Arrival at ED**
999 call		Median (IQR) (n N)	Median (IQR) (n N)	Median (IQR) (n N)	Median (IQR)	Median (IQR)

					(n N)	(n N)
On-scene attendance	Median (IQR) (n N)		Median (IQR) (n N)	Median (IQR) (n N)	Median (IQR) (n N)	Median (IQR) (n N)
Randomisation Capillary Lactate	Median (IQR) (n N)	Median (IQR) (n N)		Median (IQR) (n N)	Median (IQR) (n N)	Median (IQR) (n N)
Treatment box opening	Median (IQR) (n N)	Median (IQR) (n N)	Median (IQR) (n N)		Median (IQR) (n N)	Median (IQR) (n N)
Left Scene*	Median (IQR) (n N)	Median (IQR) (n N)	Median (IQR) (n N)	Median (IQR) (n N)		Median (IQR) (n N)
Arrival at ED**	Median (IQR) (n N)	Median (IQR) (n N)	Median (IQR) (n N)	Median (IQR) (n N)	Median (IQR) (n N)	

*Added in v4.0 of pre-hospital CRF (active in all sites from 29th August 2019)

**These numbers are lower than the totals of randomised participants due to deaths on-scene or during transit to hospital.

Appendix D2b: Mode of transport by IDS

Mode of transport	Midlands Air Ambulance (MAA) (N=)	MAGPAS (N=)	The Air Ambulance Service (TAAS) (N=)	East Anglian Air Ambulance (EAAA) (N=)	
Air	n (%)	n (%)	n (%)	n (%)	
Ground	n (%)	n (%)	n (%)	n (%)	
Missing	n (%)	n (%)	n (%)	n (%)	

Appendix D3: Description of the interventions

Not applicable

Appendix D4: Adherence to allocated intervention

		PHBP	Crystalloid	Total
Number received intervention (n) ¹				
	Yes, n(%)	n (%)	n (%)	n (%)
	No, n(%)	n (%)	n (%)	n (%)
	Missing, n(%)	n (%)	n (%)	n (%)
No. units of PRBC given				
	0, n(%)	n (%)		n (%)
	1, n(%)	n (%)		n (%)
	2, n(%)	n (%)		n (%)
	Missing, n(%)	n (%)		n (%)

No. units of LyoPlas given				
	0, n(%)	n (%)		n (%)
	1, n(%)	n (%)		n (%)
	2, n(%)	n (%)		n (%)
	Missing, n(%)	n (%)		n (%)
No. units of saline given				
	0, n(%)		n (%)	n (%)
	1, n(%)		n (%)	n (%)
	2, n(%)		n (%)	n (%)
	Missing, n(%)		n (%)	n (%)
Total number of units given (n)				
	0, n(%)	n (%)	n (%)	n (%)
	1, n(%)	n (%)	n (%)	n (%)
	2, n(%)	n (%)	n (%)	n (%)
	3, n(%)	n (%)	n (%)	n (%)
	4, n(%)	n (%)	n (%)	n (%)
	Missing n(%)	n (%)	n (%)	n (%)
Total number of units given (n)				
	All 4 units, n(%)	n (%)	n (%)	n (%)
	1-3, n(%)	n (%)	n (%)	n (%)
	No units, n(%)	n (%)	n (%)	n (%)
	Missing	n (%)	n (%)	n (%)
Per-protocol population (n)				
Received at least one unit of allocated intervention ² , n(%)	Yes, n(%)	n (%)	n (%)	n (%)
	No, n(%)	n (%)	n (%)	n (%)

¹ This is the number of participants receiving at least one unit of intervention.

² The per-protocol population is defined in section 5.4

Reasons for non-adherence will be provided.

Appendix D5: Protocol deviations

Protocol deviation	PHBP (N=)	Crystalloid (N=)

Appendix D6: Primary outcome results

The primary outcome is a composite measure consisting of episode mortality and lactate clearance.

Composite outcome, n (%)	PHBP (N=)	Crystalloid (N=)	Relative Risk ¹ (95%CI)	p-value

Yes				
No				
Missing				

¹Output from log-binomial regression model adjusted for IDS. Values of relative risk <1 indicate fewer negative events (episode mortality or failure to clear lactate concentration) with PHBP.

Composite outcome, n (%)	PHBP (N=)	Crystalloid (N=)	Absolute Risk Difference ¹ (95%CI)	p-value
Yes				
No				
Missing				

¹Output from a binomial regression model with an identity link adjusted for IDS. Values of absolute risk difference <0 indicate fewer negative events (episode mortality or failure to clear lactate concentration) with PHBP.

Appendix D6a: Qualifying event for primary outcome

Qualifying Event for Primary Outcome	PHBP (N=)	Crystalloid (N=)	Total (N=)
Both episode mortality and failure to clear lactate	n (%)	n (%)	n (%)
Episode mortality alone	n (%)	n (%)	n (%)
Failure to clear lactate alone	n (%)	n (%)	n (%)
Missing/Not available	n (%)	n (%)	n (%)

Appendix D7: Secondary outcomes results

Outcome	Time-point	PHBP (N=)	Crystalloid (N=)	Adjusted treatment effect and 95%CI	p-value
Episode Mortality ¹	Up to discharge from acute care	n/N (%)	n/N (%)	Relative risk (95% CI) ²	p-value
Episode Mortality ¹	Up to discharge from acute care	n/N (%)	n/N (%)	Absolute risk difference (95% CI) ³	
Failure to achieve lactate clearance ⁴	2 hours post-randomisation	n/N (%)	n/N (%)	Relative risk (95% CI) ⁵	p-value
Failure to achieve lactate clearance ⁴	2 hours post-randomisation	n/N (%)	n/N (%)	Absolute risk difference (95% CI) ⁶	
All-cause mortality	Within 3 hours of randomisation	n/N (%)	n/N (%)	Relative risk (95% CI) ⁷	p-value
All-cause mortality	Within 3 hours of randomisation	n/N (%)	n/N (%)	Absolute risk difference (95% CI) ⁸	
All-cause mortality	Within 3 hours of randomisation ⁹	n/N (%)	n/N (%)	Relative risk (95% CI) ⁷	p-value
All-cause mortality	Within 3 hours of randomisation ⁹	n/N (%)	n/N (%)	Absolute risk difference (95% CI) ⁸	
All-cause mortality	Within 30 days of randomisation	n/N (%)	n/N (%)	Relative risk (95% CI) ⁷	p-value
All-cause mortality	Within 30 days of randomisation	n/N (%)	n/N (%)	Absolute risk difference (95% CI) ⁸	
Pre-hospital time	Time to ED arrival from 999 call	(N ..) Mean (SD)	(N ..) Mean (SD)	Mean difference (95% CI) ¹⁰	p-value
Pre-hospital time	Time to ED arrival from randomisation	(N ..) Mean (SD)	(N ..) Mean (SD)	Mean difference (95% CI) ¹⁰	p-value
Pre-hospital fluid type and volume					
Type & Total volume of Fluids given prior to intervention	Prior to intervention up to ED arrival	(N ..) Mean (SD)	(N ..) Mean (SD)	Mean difference (95% CI) ¹¹	p-value
Type & Total volume of Fluids given post intervention	Post intervention up to ED arrival	(N ..) Mean (SD)	(N ..) Mean (SD)	Mean difference (95% CI) ¹¹	p-value
Vital Signs					
Systolic blood pressure	On-scene, ED arrival, 2, 6, 12, 24 hours after ED arrival	(N ..) Mean (SD)	(N ..) Mean (SD)	Mean difference (95% CI) ¹²	p-value
Diastolic blood pressure	On-scene, ED arrival, 2, 6, 12, 24 hours after ED arrival	(N ..) Mean (SD)	(N ..) Mean (SD)	Mean difference (95% CI) ¹²	p-value
Heart rate	On-scene, ED arrival, 2, 6, 12, 24 hours after ED	(N ..) Mean (SD)	(N ..) Mean (SD)	Mean difference (95% CI) ¹³	p-value

	arrival				
Capillary Oxygen Saturation	On-scene, ED arrival, 2, 6, 12, 24 hours after ED arrival	(N ..) Mean (SD)	(N ..) Mean (SD)	Mean difference (95% CI) ¹⁴	p-value
Respiratory rate	On-scene, ED arrival, 2, 6, 12, 24 hours after ED arrival	(N ..) Mean (SD)	(N ..) Mean (SD)	Mean difference (95% CI) ¹⁵	p-value
Other					
Venous/arterial lactate concentration	2 hours after randomisation, ED arrival, 2 hours after ED arrival	(N ..) Mean (SD)	(N ..) Mean (SD)	Mean difference (95% CI) ¹⁶	p-value
Trauma-induced coagulopathy (INR>1.5)	ED arrival, 2, 6 hours after arrival at ED	n/N (%)	n/N (%)	Relative risk (95% CI) ¹⁷	p-value
Haemoglobin concentration	ED arrival	(N ..) Mean (SD)	(N ..) Mean (SD)	Mean difference (95% CI) ¹⁸	p-value
Cumulative total blood product receipt	6, 12 and 24 hours after arrival at ED	Mean (SD)	Mean (SD)	Mean difference (95% CI) ¹¹	p-value
ARDS	Within 7 days after ED admission	n/N (%)	n/N (%)	Relative risk (95% CI) ¹⁹	p-value
Transfusion-related complications	24 hours after arrival at ED	n/N (%)	n/N (%)	Relative risk (95% CI) ²⁰	p-value
Organ Failure Free Days (OFFS)	Up to day 30	(N ..) Mean (SD)	(N ..) Mean (SD)	Mean difference (95% CI) ²¹	p-value
ROTEM					
EXTEM					
A05 (mm)	First blood sample taken in hospital	(N ..) Mean (SD)	(N ..) Mean (SD)	Mean difference (95% CI) ²²	p-value
CFT (seconds)	First blood sample taken in hospital	(N ..) Mean (SD)	(N ..) Mean (SD)	Mean difference (95% CI) ²³	p-value
MCF (mm)	First blood sample taken in hospital	(N ..) Mean (SD)	(N ..) Mean (SD)	Mean difference (95% CI) ²⁴	p-value
CT (seconds)	First blood sample taken in hospital	(N ..) Mean (SD)	(N ..) Mean (SD)	Mean difference (95% CI) ²⁵	p-value
a angle (degree)	First blood sample taken in hospital	(N ..) Mean (SD)	(N ..) Mean (SD)	Mean difference (95% CI) ²⁶	p-value
Ly30 (%)	First blood sample taken in hospital	(N ..) Mean (SD)	(N ..) Mean (SD)	Mean difference (95% CI) ²⁷	p-value
Ly60 (%)	First blood sample taken in hospital	(N ..) Mean (SD)	(N ..) Mean (SD)	Mean difference (95% CI) ²⁸	p-value
FIBTEM					
A05 (mm)	First blood sample taken in hospital	(N ..) Mean (SD)	(N ..) Mean (SD)	Mean difference (95% CI) ²²	p-value
CFT (seconds)	First blood sample taken in hospital	(N ..) Mean (SD)	(N ..) Mean (SD)	Mean difference (95% CI) ²³	p-value
MCF (mm)	First blood sample taken in hospital	(N ..) Mean (SD)	(N ..) Mean (SD)	Mean difference (95% CI) ²⁴	p-value
CT (seconds)	First blood sample taken in hospital	(N ..) Mean (SD)	(N ..) Mean (SD)	Mean difference (95% CI) ²⁵	p-value
a angle (degree)	First blood sample taken in hospital	(N ..) Mean (SD)	(N ..) Mean (SD)	Mean difference (95% CI) ²⁶	p-value
Ly30 (%)	First blood sample taken in hospital	(N ..) Mean (SD)	(N ..) Mean (SD)	Mean difference (95% CI) ²⁷	p-value

Ly60 (%)	First blood sample taken in hospital	(N ..) Mean (SD)	(N ..) Mean (SD)	Mean difference (95% CI) ²⁸	p-value
Multiplate (Area under Curve)					
TRAP	First blood sample taken in hospital	(N ..) Mean (SD)	(N ..) Mean (SD)	Mean difference (95% CI) ²⁹	p-value
ADP	First blood sample taken in hospital	(N ..) Mean (SD)	(N ..) Mean (SD)	Mean difference (95% CI) ²⁹	p-value
ASPI	First blood sample taken in hospital	(N ..) Mean (SD)	(N ..) Mean (SD)	Mean difference (95% CI) ²⁹	p-value
Exploratory					
ITU length of stay	Up to discharge from ITU	(N ..) Mean (SD)	(N ..) Mean (SD)	Mean difference (95% CI) ³⁰	
Hospital length of stay	Up to discharge from hospital	(N ..) Mean (SD)	(N ..) Mean (SD)	Mean difference (95% CI) ³⁰	
Any Organ Failure by system (SOFA ≥3)					
Respiratory	During hospital stay (up to day 30)	n/N (%)	n/N (%)	Relative risk (95% CI) ³¹	
Neurological	During hospital stay (up to day 30)	n/N (%)	n/N (%)	Relative risk (95% CI) ³¹	
Cardiovascular	During hospital stay (up to day 30)	n/N (%)	n/N (%)	Relative risk (95% CI) ³¹	
Liver	During hospital stay (up to day 30)	n/N (%)	n/N (%)	Relative risk (95% CI) ³¹	
Coagulation	During hospital stay (up to day 30)	n/N (%)	n/N (%)	Relative risk (95% CI) ³¹	
Renal	During hospital stay (up to day 30)	n/N (%)	n/N (%)	Relative risk (95% CI) ³¹	
Use of tranexamic acid	2, 6, 12 and 24 hours after arrival at ED	n/N (%)	n/N (%)	Relative risk (95% CI) ³²	
Surgery	2, 6, 12 and 24 hours after arrival at ED	n/N (%)	n/N (%)	Relative risk (95% CI) ³³	

¹mortality between time of injury/recruitment and discharge from the primary receiving facility to non-acute care

²Relative risk < 1 indicates fewer episode mortality events with PHBP

³Absolute risk difference < 0 indicates fewer episode mortality events with PHBP

⁴a failure to achieve lactate clearance \geq 20% per hour in the first 2 hours after randomisation

⁵Relative risk < 1 indicates fewer lactate clearance failures with PHBP

⁶Absolute risk difference < 0 indicates fewer lactate clearance failures with PHBP

⁷Relative risk < 1 indicates fewer mortality events with PHBP

⁸Absolute risk difference < 0 indicates fewer mortality events with PHBP

⁹Based only on participants providing an exact time of death.

¹⁰Difference < 0 indicates shorter time from 999 call or randomisation to ED arrival with PHBP.

¹¹Difference < 0 indicates less fluid administered with PHBP.

¹²Difference > 0 indicates higher blood pressure with PHBP.

¹³Difference > 0 indicates higher heart rate with PHBP.

¹⁴Difference > 0 indicates higher capillary oxygen saturation with PHBP.

¹⁵Difference > 0 indicates higher respiratory rate with PHBP.

¹⁶Difference < 0 indicates lower venous lactate concentration with PHBP.

¹⁷Relative risk < 1 indicates lower rate of trauma-induced coagulopathy with PHBP

¹⁸Difference < 0 indicates lower haemoglobin concentration with PHBP.

¹⁹Relative risk < 1 indicates lower rate of ARDS with PHBP

²⁰Relative risk < 1 indicates lower rate of transfusion-related complications with PHBP.

²¹Difference > 0 indicates higher number of days free from organ failure with PHBP

- ²² Difference > 0 indicates higher amplitude after 5 minutes with PHBP.
- ²³ Difference < 0 indicates lower clot formation time with PHBP.
- ²⁴ Difference > 0 indicates higher maximum clot firmness with PHBP.
- ²⁵ Difference < 0 indicates lower coagulation time with PHBP.
- ²⁶ Difference < 0 indicates lower speed of clot formation time with PHBP.
- ²⁷ Difference < 0 indicates lower lysis index at 30 minutes with PHBP.
- ²⁸ Difference < 0 indicates lower lysis index at 60 minutes with PHBP.
- ²⁹ Difference > 0 indicates higher agonist AUC with PHBP.
- ³⁰ Difference > 0 indicates longer length of stay with PHBP.
- ³¹ Relative risk < 1 indicates fewer organ failure events with PHBP.
- ³² Relative risk < 1 indicates lower rate of tranexamic acid use with PHBP.
- ³³ Relative risk < 1 indicates lower rate of surgery with PHBP.

